### 2.2.7. Reproductive Toxicity

VOR rapidly crossed the placenta in both the rat and rabbit, following administration of a dose of 15 mg/kg/day and 150 mg/kg/day, respectively (<1 times the human exposure based on AUC0-24) and reached transplacental equilibrium within 30 minutes post-dose.

Reproductive toxicity studies were conducted in male and female rats to determine potential effects of dosing with VOR for more than 20 days, and up to 26 weeks, on fertility and reproduction. In male rats, there were no treatment-related effects on mating performance, fertility, embryonic/fetal survival, sperm count and motility, testicular weight, or testicular and epididymal histomorphology in any drug-treated group. The NOEL for effects on female fertility was  $\geq 150$  mg/kg/day ( $\geq 900$  mg/m^2/day). The NOEL for effects on female reproductive performance, however, as determined by increases in the number of corpora lutea, was <15 mg/kg/day (<90 mg/m^2/day), which is below the equivalent human dose expressed on an equivalent surface area basis (250 mg/m^2/day).

VOR was evaluated in a panel of genetic toxicity assays; in vitro assays were found to be positive. No human safety data for the use of VOR during pregnancy are available.

## 2.3. HIV-SPECIFIC EX VIVO EXPANDED T CELL THERAPY (HXTC)

### 2.3.1. T cell Therapy in HIV-Infected Individuals

Support for this phase I study is derived from studies demonstrating the feasibility and safety of infusing PLWH with ex vivo-expanded HIV-specific CTLs that were specific for 1-3 epitopes of Gag, Pol, or Nef [45-47, 75, 76]. The earliest study of

expanded HXTCs in actively viremic participants found that infusion with up to  $10^{10}$  non-specifically activated, expanded autologous CD8+ T cells was safe and tolerable with no CTL related adverse events in 5 participants with AIDS, but enhancement of HIV specific cytotoxicity post-infusion was transient and no impact on virologic outcome was found [77, 78]. In another pilot study of actively viremic participants with CHI, autologous administration of CD8+ CTLs primed to express cytotoxicity against HIV-1 epitopes gp120, gag p17, p24m, and nef produced no toxicity or clinical deterioration over six months of follow-up [46]. Three of six participants showed improvements in plasma HIV RNA levels or CD4+ count at six months despite low enrollment CD4+ counts (100-400 c/mm^3). Two additional studies of one patient each who received an infusion of CTL clones against Gag and Nef, respectively, did not find any impact on viremia due to the short lived nature of the Gag clone and development of HIV escape variants to the Nef clone, but did find that the infusion was safe and well-tolerated [75, 79]. Another small study in three participants on ART but with low level viremia established the safety and tolerability of escalating doses of gag-specific CTL clones of up to  $3.3 \times 10^9/m^2$  [45]. Transferred HIV-specific CTLs migrated to lymph nodes where they co-localized with HIV RNA+ cells in the parafollicular regions. The presence of CTL clones in the peripheral blood correlated with a significant but transient reduction in the number of HIV-infected peripheral CD4+ T cells. In all of these studies, the only adverse event reported was mild and transient chills and rigors following infusion. These studies established the feasibility and safety of adoptive transfer of HIV-specific CTL clones, but showed only modest results. Notably, these studies were performed in actively viremic HIV-infected participants, and infused cells were generally monoclonal and had been expanded extensively in vitro, hence were likely highly differentiated. In a more recent study, HIV-specific CD8+ T cell clones derived from the central memory population of chronically HIV-infected participants on suppressive ART were expanded in vitro, and following autologous re-infusion could be detected for up to 84 days in blood and rectal tissue and retained or re-expressed memory markers (CD28+, CD62L+) and function (secretion of IL-2 and proliferation on cognate Ag exposure) [47]. Virologic outcomes were not assessed in this study, however. In contrast to the latter study, we will break new ground by generating polyclonal CD4+ and CD8+ T cells specific for multiple HIV epitopes in multiple antigens.

Among these studies and others with HIV-specific T cells, the only adverse events reported were mild and transient fever, arthralgias, myalgias, chills, and rigors following the infusions [45-47, 75-79]. Some of these events were associated with the administration of exogenous IL-2 given in conjunction with T cell infusion. This suggests that it will be safe and perhaps more effective to target these three antigens simultaneously in one T cell product, as proposed with this study. Furthermore, we hypothesize that our HXTCs will be safely tolerated in participants that have been on stable ART with undetectable viral load based on the rationale that these early studies demonstrated the safety of infusing CTLs in higher risk groups including viremic and HIV-infected participants with advanced immunosuppression.

Despite infusing T cells with very limited specificity in order to target a highly mutable virus, only one study showed a single instance of the emergence of escape variants in a severely immunocompromised AIDS patient [79]. Though this demonstrates that escape variants are a low risk, we are further lessening this risk by proposing to infuse broadly-specific T cells. Importantly, not all previous studies excluded the presence of CD4+ T cells in the product and this did not result in increased HIV RNA levels post-infusion. Although CD4+ HIV-specific T cells may be subject to elimination by HIV infection, this risk is lessened by administration only to participants with durable viral suppression on ART, and if functionality and persistence is observed in this phase I study, HIV-specific T cells could be rendered resistant to HIV infection prior to infusion in subsequent trials. The fact that almost all participants who are suppressed on ART have low level (and stable) detectable viremia gives us a quantifiable endpoint following autologous T cell infusion without having to stop therapy in these participants. An impact on low level viremia as measured by a single copy assay (SCA) would be the first signal that these *ex vivo* enhanced and expanded T cells are having an effect. Taken altogether, the previous human experience with the infusion HIV-specific T cells supports the feasibility and of our novel strategy of polyclonal CD4+ and CD8+ T cells specific for multiple HIV epitopes in multiple antigens in participants with viral suppression on ART.

### 2.3.2. Safety and Efficacy of antigen specific HIV-specific T cell (HXTC) therapy in humans

Under IND 15984 (HXTC study), we have successfully infused HIV-specific *ex-vivo* expanded T cells (HXTCs) in four PLWH on suppressive ART to date. The HXTCs were well tolerated with no SAEs reported in any of the participants, with the most common non-serious AE being a transient altered taste during HXTC infusion (expected with DMSO-containing infusions).

Our group has over a decade of experience with safely and effectively treating immunocompromised patients post-transplant with virus-specific T cells and tumor-specific T cells that are manufactured using similar protocols to the HXTC product. Prior work by several groups has demonstrated that CMV, EBV, and adenovirus-specific T cells, including T cells generated using overlapping peptide pools, provide a safe and effective treatment and prophylaxis for viral infections and post-transplant lymphoproliferative disorder (PTLD) in immunocompromised patients post-transplant (**Table 1**).

**Table 1: Human Experience-Related INDs, and protocols from co-investigator [name] and colleagues.**

**IND 5049** - Administration of EBV specific cytotoxic T lymphocytes to recipients of mismatched-related or phenotypically similar unrelated donor marrow grafts (ETNA).

**IND 6387** – Administration of neomycin resistance gene marked EBV specific cytotoxic T-lymphocytes to patients with relapsed EBV- positive Hodgkin disease (ANGEL).

**IND 11186** - Virus specific cytotoxic T-lymphocytes for the prophylaxis of CMV after allogeneic stem cell transplant: a dose-finding trial (VICTA).

**IND 12830** – Administration of TGF- $\beta$  resistant LMP2a-specific cytotoxic T-lymphocytes to patients with relapsed EBV-positive lymphoma (TGFb).

**IND 11835** - Administration of virus-specific cytotoxic T-lymphocytes for the prophylaxis and therapy of adenovirus infection post allogeneic stem cell transplant (LYPTAIST).

**IND 13958** - Phase I/II study of the administration of multi-virus-specific cytotoxic T lymphocytes (CTLS) expressing CD19 chimeric receptors for prophylaxis of therapy of relapse of acute lymphoblastic leukemia post hemopoietic stem cell transplantation (MULTIPRAT).

**IND 14714** - Administration of Tumor-Associated Antigen (TAA)-specific Cytotoxic T-lymphocytes to patients with active or relapsed Hodgkin or non-Hodgkin Lymphoma (TACTAL)

**IND 15086** - Administration of rapidly generated LMP, BARF1 and EBNA1 specific Cytotoxic T-lymphocytes to patients with EBV+ Lymphoma (GRALE)

**IND 15092** - Administration of Rapidly Generated Multivirus-Specific Cytotoxic T-Lymphocytes for the Prophylaxis and Treatment of EBV, CMV, Adenovirus, HHV6, and BK virus infections post Allogeneic Stem Cell Transplant (ARMS)

**IND 15714** - Adoptive Transfer of Cord Blood T cells to Prevent and Treat CMV, EBV, and Adenovirus Infections after Transplantation (ACTCAT2)

**IND 15779** - Multivirus-Specific Cytotoxic T-Lymphocytes for the Prophylaxis and Treatment of EBV, CMV, and Adenovirus Infections post Allogeneic Stem Cell Transplant (MUSTAT)

**IND 15779** - Administration of Most Closely HLA-matched Multivirus-specific Cytotoxic T-Lymphocytes for the Treatment of EBV, CMV, Adenovirus Infections Post Allogeneic Stem Cell Transplant (CHAPS)

**IND 15779** - Treatment of EBV, CMV, and Adenovirus Infections in Primary Immunodeficiency Disorders with Viral-specific Cytotoxic T-Lymphocytes (TREPID)

**IND 15772** – Administration of LMP-Specific Cytotoxic T-Lymphocytes to Patients with Relapsed EBV-Positive Lymphoma (ALC12)

### 2.3.3. Virus specific Cytotoxic T Lymphocytes after allogeneic hematopoietic stem cell transplantation

At St. Jude Children's Research Hospital and Baylor College of Medicine (IND 5049), more than 100 allogeneic HSCT recipients received donor-derived ex vivo expanded EBV-CTLs. The only agent-related adverse events were inflammatory reactions at tumor sites; this was marked in one bone marrow transplant (BMT) recipient with bulky disease at the time of CTL administration and milder in three BMT recipients with subclinical disease (IND 5049).

Subsequently, allogeneic trivirus-(BCM IND 11186), and bivirus-specific (**BCM IND 11835**) CTL derived from HLA-matched related, HLA-mismatched related and HLA-matched unrelated donors (NHLBI-PACT project 00014) were administered to over 40 patients both as prophylaxis and as treatment of viral infections. No adverse events were attributable to the T-cell infusions. None developed more than grade 2 GVHD or other toxicities over the 3 months of safety monitoring after infusion. This study demonstrated that multi-virus-specific T-cells derived from the peripheral blood of seropositive donors were able to expand in vivo and mediate activity against multiple viral reactivations from a single product.

To increase the safety and decrease the manufacturing time of virus-specific T-cells, [name] and colleagues while at Baylor replaced EBV-transformed B-cell lines and adenoviral vectors as a source of viral antigens with overlapping peptide libraries (pepmixes) spanning the entire protein sequence of protective antigens (those that induce T-cells with protective capacity) from viruses including EBV, CMV, adenoviruses, BK, and HHV6. Large numbers of multi-virus-specific T-cells can be produced after a single stimulation of peripheral blood mononuclear cells (PBMCs) with combined pepmixes. These have been infused in >20 allogeneic HSCT recipients (IND 15092 (Baylor) and IND 15779 (CNMC)). There were no immediate infusion-related toxicities with one incidence of grade 2 GVHD. The polyspecific VSTs expanded in vivo and produced clinical responses in all patients.

### 2.3.4. Safety and Efficacy of Autologous T-cell therapies for EBV positive Lymphoma

Under **IND 6387**, the [name] group at the Center for Cell and Gene Therapy (CAGT) at Baylor College of Medicine generated CTL enriched for effector cells specifically targeting LMP antigens (LMP2 +/- LMP1) and administered them to patients with EBV+ lymphoma. No immediate toxicity was observed. After CTL infusion, increased numbers of LMP-specific T-cells were detected in the blood, (range 2 to 70 fold) persisting for up to 3 months. In conclusion, immunotherapy with CTL targeting LMP antigens is well tolerated in patients with EBV+ lymphoma, and can induce complete and sustained clinical responses in 62% of patients. This demonstrated that the anti-

tumor activity of ineffective circulating tumor-specific T cells could be restored by ex vivo activation and expansion.

[name] and colleagues have also modified T cell manufacturing for EBV-positive lymphoma patients. Dendritic cells loaded with overlapping peptide libraries spanning 4 EBV antigens were used for the first stimulation of T-cells in the presence of cytokines, and pepmix-pulsed, autologous activated T-cells combined with K562 cells expressing co-stimulatory molecules as transgenes were used for a second stimulation. Such T cells have been used safely in >9 individuals with multiple relapsed lymphoma, resulting in increases in the frequency of EBV-specific T-cells, producing tumor responses and no adverse events. This manufacturing protocol is similar to the manufacturing of HXTCs proposed here, suggesting that the adoptive transfer of HXTCs in patients with HIV should also have an excellent safety profile.

## 2.4. POTENTIAL BENEFITS

The addition of VOR and HIV-specific ex vivo expanded T cells (HXTCs) to a person's ART regimen or the donation of one's blood cells to this research project provide no direct medical benefits to participants. However, participation makes it possible to continue research on HIV, potentially resulting in new treatments for HIV infection. Due to the intensive, demanding nature of study follow-up, administration of experimental product and multiple leukapheresis time points, we will provide an IRB-approved compensation to participants.

## 3. OBJECTIVES

### 3.1. Study Objectives

#### 3.1.1. Primary Objectives

- 3.1.1.1. Evaluate the safety of serial administration of VOR followed by autologous ex vivo expanded HIV-1 specific T-cells (HXTC) therapy in participants maintained on suppressive combination antiretroviral therapy (ART)
- 3.1.1.2. Evaluate the association of serial VOR dosing and serial HXTC therapy on the frequency of resting CD4 T cell infection (IUPM) via quantitative viral outgrowth (QVOA) in participants who complete the leukapheresis procedure (#2) in Step 6.

#### 3.1.2. Secondary Objectives

- 3.1.2.1. Explore the ability of combination VOR and HXTC therapy to increase HIV-1 specific immune responses in participants maintained on suppressive ART.

#### 3.1.3. Other Outcome Measures

- 3.1.3.1. Explore the influence of HXTC therapy combined with serial VOR doses on low-level plasma viremia as measured by single copy assay (SCA) in participants who maintained suppression on ART.
- 3.1.3.2. Explore the impact of VOR and HXTC therapy on the ability of CD8 T cells to enhance clearance of latently infected cells as they emerge from latency in a latency clearance assay.
- 3.1.3.3. Explore the impact of VOR and HXTC therapy on integrated proviral DNA quantification.
- 3.1.3.4. Explore the impact of VOR and HXTC therapy on the presence and persistence of T cell escape variants within the latent reservoir

### 3.2. Study Outcome Measures

#### 3.2.1. Primary

The primary outcome will be safety and tolerability of administration of VOR combined with HXTC therapy.

#### 3.2.2. Secondary

The secondary outcome will be the impact of VOR and HXTC therapy on the HIV-specific immune response and on the frequency of latent HIV infection, as measured by a QVOA and plasma HIV-1 RNA viremia measured by SCA, an assay with a limit of quantitation of 1 copy/mL.

## 4. STUDY DESIGN

This is a phase I, single-site, study to evaluate the effects of VOR and HIV-1 Antigen Expanded Specific T Cell Therapy (HXTC) on persistent HIV-1 Infection in HIV-infected individuals suppressed on ART. Overall, twelve participants with durable viral suppression will be enrolled and will complete the study. All participants will be dosed with HXTC and VOR. Participants will continue their baseline ART regimen throughout the study.

#### 4.1. Step 1 (Visits 1 and 2) – Screening, Enrollment, and Baseline Leukapheresis procedure (Leuk #1)

During the screening visit, all participants will have the study explained and the informed consent signed. After the informed consent process is completed, participants will be screened for the study and those who meet eligibility requirements will enroll (Visit 2) and have their white blood cells collected via a leukapheresis procedure (Leuk #1). A baseline measurement for the frequency of HIV-1 infection per million resting CD4+ cells (IUPM) of  $\geq 0.3$  by QVOA allows participants to progress to Step 3, Visit 5.

*Note: Participants who exhibited an IUPM  $\geq 0.3$  in prior UNC IRB-approved studies, will be required to complete the baseline leukapheresis after meeting the eligibility criteria and enrolling. However, they will not be required to wait for results of the baseline leukapheresis IUPM measurement to move to Step 3 for collection of blood samples for the manufacturing of HXTCs.*

**4.2. Step 2 (Visits 3 and 4) – Omitted from Version 3 of the protocol (V3.0)**

**4.3. Step 3 (Visits 5 and 6) – Production of HXTc Therapy and Pre-Dose Safety Assessment for Initiation of Combination Therapy**

At Step 3, Visit 5, collect up to 245 mL of blood and send ambient temperature overnight to the Program for Cell Enhancement and Technologies for Immunotherapy (CETI) at Children's National Hospital (CNH) in Washington, DC for the manufacturing of HXTCs and HLA testing. This manufacturing process takes approximately 8 weeks.

Participants who participated in studies conducted under IND 15984 (IRB# 17-0468 and IRB# 14-0741) with HXTc cells already produced and stored at CNH, with documentation that adequate cells are available for infusions, can bypass Step 3, Visits 5 and 6 and progress directly to Step 4.

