**4.4. Step 4 (Visits 7 – 13) – 1st Series of 10 Doses of VOR with 2 Infusions of HXTCs.**

Successful manufacturing of HXTc cells and acceptable clinical findings during the pre-dose safety assessment at Step 3, Visit 6 determine advancement to Step 4.

Participants receive 10 doses of VOR 400 mg PO every 72 hours. At study Visits 7 and 10, approximately 6 hours after their VOR dose, they will receive an HXTc infusion of up to  $1 \times 10^8$  cells/m^2. Thus, each participant receives ten VOR 400 mg doses and two HXTc infusions (HXTc #1 and #2) in Step 4.

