## 6. STUDY INTERVENTION

### 6.1 HXTC

#### 6.1.1. Collection of 100 mL of Blood

Participants will have 100 mL of blood drawn at Step 3, Visit 5 to make the study product. These whole blood samples are shipped ambient temperature overnight to the CETI Processing Facility at CNH in Washington, DC. This shipment also includes an additional sample for HLA analysis.

If the participant previously participated in another study protocol at UNC and has sufficient product already manufactured under IND 15984, the study will not require an additional blood sample and will use the previously manufactured and stored HXTCs.

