#### **6.2.3. Dosage, Preparation, and Administration of VOR**

The UNC IDS Pharmacy stores, distributes, and maintains accountability for VOR. The dispensing of each dose will be participant specific and by signed prescription. Upon receipt of the VOR doses from IDS, the study coordinator dispenses VOR to the participant in the research clinic according to the dose, schedule, and supportive care guidelines.

Take each VOR dose with food.

The primary IDS pharmacist will be responsible to the principal investigator for maintaining study drug accountability, reconciliation, and record maintenance during the study, including documentation of the amount of study treatments (VOR) received in IDS and the amount administered to each participant.

Participants will be provided their first dose of VOR 400 mg in Step 3, Visit 6 to take 4 in Step 4, Visit 7. Participants will take this dose at home in the morning prior to coming for Visit 7. The study coordinator will provide participants with individualized dosing instructions, clearly identifying the days they are required to take VOR. The study coordinator will contact participants on each dosing day. Participants will be instructed to contact the study coordinator and be prepared to return to the clinic should any adverse event evolve. Participants will be monitored for the development of toxicities. Participants will take the doses approximately 72 hours apart.

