### 7.3.2.2. **Visit 6 – Pre-Dose Safety Assessment Visit for Step 4**

Schedule Visit 6 after CNH verifies that product manufacturing is complete. The pre-dose visit will be  $\leq$  21 days prior to Step 4, Visit 7 (Study Week 0).

The pre-dose safety labs must be reviewed and signed off by the study PI or designee prior to Visit 7. If the participant does not meet one or more of the pre-dose safety lab assessments, repeat of the abnormal lab values can occur one time only. If repeat values are within the pre-dose safety lab assessment criteria, participants receive VOR and HXTc infusions at Visit 7.

After repeat testing, participants with any lab values that remain outside the guidelines below but are considered clinically non-significant and documented as such by the study PI (or designee), may proceed to the dosing/infusion visit after review and approval of the case by the protocol and/or safety committee.

Please reference the SOE for clinical and research procedures done at this visit.

Hematology	Laboratory Value
ANC	$\geq$ 1,500 /mcL
Platelets	$\geq$ 125,000 / mcL
Hemoglobin	$\geq$ 12 g/dL (male) and $\geq$ 11.0 g/dL (females)
Chemistry	
K + levels	WNL
Mg ++ levels	WNL
Glucose	$\leq$ Grade 1 (fasting or non-fasting)
Renal	
Creatinine	$<1.3 \times$ ULN
Hepatic	

Total bilirubin	< 1.1 times the ULN range. If total bilirubin is elevated, direct bilirubin must be < 2 times the ULN range.
AST (SGOT) and ALT (SGPT)	< 1.25 X ULN
Alkaline Phosphatase	<1.25 X ULN
Other Testing	
Serum pregnancy test (all females)	Negative
RPR	No active infection
HIV RNA	<50 copies/ml
CD4	≥350
HBsAg and HCV Ab	Negative or not detectable Note: positive HCV Ab will reflex to an HCV RNA. In this scenario, a negative HCV RNA will qualify participant.

Estimated Blood Volume: up to 120 mL

At this visit, participants will be given 1 dose of VOR 400 mg to take home. Upon verification of acceptable labs, participants will be contacted to verify date and time of Visit 7 and also to verify the time participant is to take the first dose of VOR that morning. Plans will be made for participants to return the dose of VOR 400 mg to the study coordinator should the participant fail to have acceptable pre-dose labs for Step 4.

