#### **7.3.3. Step 4 (Visits 7 – 13) - First Series of VOR 400 mg x 10 doses and 2 HXTC infusions**

## Visit Windows for Step 4

Visit #	Visit Evaluations	Visit Window
Visit 7	VOR Dose 1 and HXTC Infusion #1	≤ 21 days after Visit 6
Visit 8	Safety check and Research Labs	1 - 3 days after Visit 7
	VOR Dose #2	3 days after Visit 7 (Dose 1 + 3 days)
Visit 9	VOR Dose #3	6 days after Visit 7 (Dose 1 + 6 days)
	VOR Dose #4	3 days after Visit 9 (Dose 1 + 9 days)
	VOR Dose #5	6 days after Visit 9 (Dose 1 + 12 days)
Visit 10	VOR Dose #6 and HXTC Infusion #2	9 days after Visit 9 (Dose 1 + 15 days)
Visit 11	Safety Check and Research Lab	1 - 3 days after Visit 10
	VOR Dose #7	3 days after Visit 10 (Dose 1 + 18 days)
	VOR Dose #8	6 days after Visit 10 (Dose 1 + 21 days)
	VOR Dose #9	9 days after Visit 10 (Dose 1 + 24 days)
Visit 12	VOR Dose #10	12 days after Visit 10 (Dose 1 + 27 days)
Visit 13	Safety F/U & Step 5 Pre-Dose Clinical Assessment	7-14 days after Visit 12

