#### 7.3.3.1.2. **Pre – HXTC INFUSION**

The participant will come to the CTRC research clinic approximately 3.5 - 4 hours after taking their dose of VOR for pre-infusion evaluations, which includes:

- Review participant allergies

- Establish IV access
- Collect research samples approximately 4 hours after AM VOR dose. Collection can be +/- one hour of the 4-hour time point.
- Clinical assessments per SOE
- Documented PI review of clinical labs from Visit 6 as well as review of clinical assessments done at this visit are required prior to the thawing and infusion of HXTC study product.

Note: Administration of HXTC can be delayed up to 1 week pending resolution of physical findings or lab abnormalities.

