8.1.1.4. Pre-Dose Lab Assessments

There are two time points in the study when the participant completes Pre-Dose Safety Lab Assessments. The lab results obtained in these assessments must be within the study established parameters for the administration of VOR to occur. Labs that fall outside the parameters can be repeated one time only to qualify participants to proceed.

After repeat testing, any lab values that remain outside the guidelines but considered clinically non-significant and documented as such by the study PI (or designee), must be reviewed and approved by the protocol and/or safety committee prior to dosing/infusion visit.

The time points of Pre-Dose Lab Assessments are:

1. Step 3, Visit 6 (1st Series of VOR doses (10) and two HXTC infusions)
2. Step 4, Visit 13 (2nd Series of VOR doses (10) and three HXTC infusions)

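### Section 4.3 lets participants with stored HXTC skip the Visit 6 pre-dose safety assessment that four other sections require before first treatment

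*Combined protocol and SAP*

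**What the plan says.** Section 4.3 covers participants from studies under IND 15984 whose HXTC is already made and stored in adequate quantity. They "can bypass Step 3, Visits 5 and 6 and progress directly to Step 4".

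Four sections make Visit 6 a condition for treatment, and none mentions stored product:

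- Section 4.4: successful manufacturing and "acceptable clinical findings during the pre-dose safety assessment at Step 3, Visit 6 determine advancement to Step 4".
- Section 7.3.2.2: "The pre-dose safety labs must be reviewed and signed off by the study PI or designee prior to Visit 7".
- Section 7.3.3.1.2, before product is thawed for infusion #1: "Documented PI review of clinical labs from Visit 6 as well as review of clinical assessments done at this visit are required".
- Section 8.1.1.4, which names Visit 6 and Visit 13 as the two pre-dose time points: "The lab results obtained in these assessments must be within the study established parameters for the administration of VOR to occur".

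Section 5.4 also lists failure of the Visit 6 requirements as a reason for not entering Step 4. Section 6.2.3 has the first vorinostat (VOR) dose handed out at Visit 6 and adds: "Participants will take this dose at home in the morning prior to coming for Visit 7". The Step 4 window table in 7.3.3 places Visit 7 "≤ 21 days after Visit 6".

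The other provision for stored product, section 6.1.1, says only that "the study will not require an additional blood sample and will use the previously manufactured and stored HXTCs".

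**The concern.** Visits 5 and 6 serve different purposes. Stored cells remove the need for the Visit 5 draw. They say nothing about a participant's current liver function, creatinine, electrolytes, viral load or CD4 count, which Visit 6 is there to check. Section 4.3 waives both visits together.

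Site staff therefore hold two incompatible instructions about the first dose. Following 4.3 means treating without the assessment that four sections require. Following those sections means disregarding 4.3. In a phase I study whose primary outcome is safety and tolerability, the text should not leave open whether pre-dose safety labs are needed.

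**Working it through.** The plan gives no figure to reproduce. The check is whether 4.3 can be read together with the other sections, and what is lost if it governs.

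**1. What remains if 4.3 governs and Visit 6 is skipped**

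| Place | What it takes from Visit 6 | What a bypassing participant has |
|---|---|---|
| 4.4 | Findings that decide entry to Step 4 | None |
| 7.3.2.2 | Labs signed off before Visit 7 | None |
| 7.3.3.1.2 | Labs reviewed before thaw and infusion #1 | None |
| 8.1.1.4 | Results in range before VOR is given | None for the first series |
| 6.2.3 | Dispensing of VOR dose 1 | No visit that dispenses it |
| 7.3.3 | Start of the Visit 7 window | No starting point |
| 8.1.1.7 | Complete physical examination | Screening examination only |

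So treating 4.3 as a special rule that overrides the general one does not make the protocol workable. The committee-approval route in 7.3.2.2 and 8.1.1.4 does not help either. It lets a participant proceed with an out-of-range value after repeat testing; it does not waive the assessment.

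**2. Whether Visit 7 supplies a substitute**

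The Visit 7 text orders a urine pregnancy test for women and otherwise relies on the Visit 6 labs. Visit 10, by contrast, has its own safety labs, drawn STAT or within 48 hours (7.3.3.4.2). The Step 4 marks in the Schedule of Events are not legible in the copy reviewed, so labs at Visit 7 cannot be excluded. The closest parallel is Visit 14, which opens the second series and relies on Visit 13 labs. Its column shows a urine pregnancy test and no chemistry or CBC. In any case, VOR dose 1 is taken at home before the participant arrives, so labs drawn at the visit could not govern that dose.

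**3. Pre-dose criteria left on screening results**

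- Rows in the 7.3.2.2 table: 3 hematology + 3 chemistry + 1 renal + 3 hepatic + 5 other = 15.
- Covered by the CBC tied to the baseline leukapheresis: ANC, platelets, hemoglobin = 3.
- Covered by the urine pregnancy test tied to Visit 7: 1.
- Remaining: 15 − 3 − 1 = 11. These are potassium, magnesium, glucose, creatinine, bilirubin, AST/ALT, alkaline phosphatase, RPR, HIV RNA, CD4 and HBsAg/HCV.

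The 11 assumes no further labs before or at Visit 7.

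**4. Age of the panel at Visit 7**

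- With Visit 6: at most 21 days (7.3.2.2 and 7.3.3).
- Without it: no maximum is stated. Section 7.1 allows the baseline leukapheresis up to 45 days after screening, so the screening panel can already be 45 days old at that point, 45 / 21 = 2.1 times the limit.
- The interval from leukapheresis to Visit 7 is not defined for this group. As an illustration only, suppose it equals the 4 to 6 weeks that the Schedule of Events places between leukapheresis and Visit 5. The panel would then be up to 45 + 28 = 73 to 45 + 42 = 87 days old. It could be younger or older, because nothing bounds it.

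**The case against.** The strongest reply is that the feared outcome is hard to reach. Dose 1 is dispensed at Visit 6, VOR may not be given unless the pre-dose labs are in range, and product may not be thawed without review of Visit 6 labs. A participant who skips Visit 6 is more likely to stall and prompt a query than to be dosed unscreened. That is right, and it limits the seriousness. It does not remove the contradiction: those same conditions are what 4.3 purports to bypass.

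A second reply is that 4.3 is a specific exception placed just before the general rule and need not be repeated everywhere. On that reading the fault is an exception not carried through. The protocol would still need replacement labs, a dispensing visit and a new window for Visit 7, and it has none.

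Three points of scale stand:

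- Screening applies the same or similar limits, and adds coagulation, albumin and lipase, so these participants have passed a comparable check once.
- The group may be very small or empty. Section 2.3.2 reports four people infused under IND 15984 to date. The current minimum dose of 5 × 10^7 cells/m² is 2.5 times the 2 × 10^7 used under versions 1 and 2, so older stock may not suffice.
- The silence of 6.1.1 on Visit 6 is weak evidence taken alone, because that section is about the blood draw. It shows only that the waiver in 4.3 finds no support there.

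**Conclusion.** The concern holds. Section 4.3 waives a pre-dose safety assessment that 4.4, 7.3.2.2, 7.3.3.1.2 and 8.1.1.4 require without exception, and no reading of 4.3 leaves a complete set of instructions for the affected participants. Followed literally, it removes the 21-day limit on the pre-dose panel and leaves 11 of 15 criteria on screening results, provided that no labs are scheduled before or at Visit 7.

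The practical risk is moderate: the group's size is not given and may be zero, and a query or deviation is the likelier result. Sample size, endpoints and analysis are unaffected. The point should be fixed because it concerns the first dose in a phase I safety study and the text as written permits the wrong course.

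**What to change.** Amend 4.3 so that participants with stored product bypass Visit 5 only. They complete Visit 6 in full (pre-dose labs, investigator sign-off and dispensing of VOR dose 1) within 21 days before Visit 7, like everyone else.

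Give Visit 6 its own trigger for this group: documentation that adequate stored cells are available. This is needed because the Schedule of Events times Visit 6 from Visit 5, which these participants do not attend. A footnote there is enough.

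The cost is one sentence in 4.3, one footnote, and one visit already planned for all other participants.

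A separate and optional clarification could go in the same edit: state that the baseline IUPM result of at least 0.3 must be available before Step 4 for this group, since the note in 4.1 lets some participants move to Step 3 before that result is known.
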